6.6.15. Check and record concomitant medication/vaccination and intercurrent medical conditions

Concomitant medication/vaccination must be checked and recorded in the eCRF as described in Section 7.6.

Intercurrent medical conditions must be checked and recorded in the eCRF as described in Section 7.7.

Recording of AEs, SAEs, pregnancies and pIMDs

- Refer to Section 9.2 for procedures for the investigator to record AEs, SAEs, pregnancies and pIMDs. Refer to Section 9.3 for guidelines on how to submit SAE, pregnancy and pIMD reports to GSK Biologicals.
- The subjects will be instructed to contact the investigator immediately should they manifest any signs or symptoms they perceive as serious.
- At each vaccination visit, diary cards will be provided to the subjects. Any unsolicited AEs (i.e. on the day of vaccination and during the next 29 days) occurring after vaccination will be recorded by all subjects. The subjects included in the safety and immune sub-cohort will also record body (axillary) temperature and any solicited local/general AEs (i.e. on the day of vaccination and during the next 6 days). In case of illiterate subjects, a designated person (such as a family member or a field worker) may provide assistance to complete the diary cards. The subject will be instructed to return the completed diary card to the investigator at a later visit. In case a diary card is lost by the subject or he/she is unable to complete the diary card, the safety information should be captured retrospectively using a descriptive interview. ***The site staff or Investigator should not write on the diary card, this information should be captured in the source notes.*** This process will be documented in a site SOP. Please refer to the SPM for further details. **(Amended: 29 January 2014)**
- Verify completed diary cards during discussion with the subject on Visits 2, 3*, 4, 5* and 6. Collect diary cards from the subjects at Visits 4 and 6. Any unreturned diary cards will be sought from the subject through telephone call(s) or any other convenient procedure. The investigator will transcribe the collected information into **Inform™** in English. *Only for subjects included in the safety and immune sub-cohort. **(Amended: 29 January 2014)**

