4.2. Secondary endpoints

Efficacy:

- Incident cases of **Definite Xpert MTB/Rif positive Pulmonary TB disease** not associated with HIV-infection, meeting the second case definition.
Over a period starting 1 month post dose 2 and lasting up to 35 months post last vaccination.
- Incident cases of **Definite Pulmonary TB disease** meeting the third case definition.
Over a period starting 1 month post dose 2 and lasting up to 35 months post last vaccination.
- Incident cases of **Microbiological Pulmonary TB disease** meeting the fourth case definition.
Over a period starting 1 month post dose 2 and lasting up to 35 months post last vaccination
- Incident cases of **Clinical TB disease** meeting the fifth case definition.
Over a period starting 1 month post dose 2 and lasting up to 35 months post last vaccination

Refer to Section 5 for case definitions.

Safety:

- Occurrence of serious adverse events (SAEs).
During the entire study period
- Occurrence of unsolicited adverse events (AEs).
During the 30-day follow-up period following vaccination (day of vaccination and 29 subsequent days after each vaccine dose)
- Occurrence of solicited local and general AEs in the safety and immunogenicity sub-cohort.
During the 7-day follow-up period following vaccination (day of vaccination and 6 subsequent days after each vaccine dose)
- Occurrence of all Potential Immune Mediated Diseases (pIMDs).
Over a period starting at Day 0 until 6 months post-dose 2.
- Occurrence of grade ≥ 2 haematological and biochemical levels, in the safety and immunogenicity sub-cohort, at:
Days 0, 7, 30 and 37.

Immunogenicity:

- Evaluation of cell-mediated immune (CMI) responses with respect to components of the study vaccine, in the safety and immunogenicity sub-cohort:
 - Determined by the frequency of M72-specific CD4+/CD8+ T-cells per million cells identified after *in vitro* stimulation, as expressing any combination of immune markers among Cluster of Differentiation-40 Ligand (CD40L), interleukin-2 (IL-2), interferon-gamma (IFN- γ) and Tumour Necrosis Factor-alpha (TNF- α)

Timepoints: prior to dose 1 (Day 0) and post dose 2 (Day 60, Years 1, 2 and 3)

- Evaluation of humoral immune responses with respect to components of the study vaccine, in the safety and immunogenicity sub-cohort:
 - Determined by M72-specific antibody titres as measured by ELISA.
 - Determined by seropositivity rates as measured by ELISA.

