11.13. Unsolicited symptoms

The proportion of subjects/doses with at least one report of unsolicited AE classified by the Medical Dictionary for Regulatory Activities (MedDRA) reported during the 30-day follow-up period (Days 0 to 29) will be tabulated with exact 95% CI by treatment group.

The same tabulations will be done for grade 3 AEs, AEs related to vaccination, grade 3 events related to vaccination and AEs resulting in a medically attended visit.

As only the subjects part of the safety and immunogenicity sub-cohort have a diary card to collect the solicited AEs, those symptoms (redness, swelling, pain at injection site, fever, headache, respiratory symptoms, malaise, myalgia)) reported for the other subjects were recorded in the Case Report Form (CRF) section on unsolicited symptoms.

Therefore to assess the impact of this situation, the following analyses will be proposed:

- The same analysis will be produced for the subjects with diary cards (part of the safety and immunogenicity sub-cohort).
- The proportion of subjects/doses with at least one report of unsolicited AE classified by MedDRA reported during the 7-day follow-up period (Days 0 to 7) will be tabulated with exact 95% CI by treatment group. Idem for grade 3 AEs, AEs related to vaccination, grade 3 events related to vaccination.
- The proportion of subjects/doses with at least one report of unsolicited AE classified by MedDRA reported after the 7-day follow-up period (Days 7 to 29) will be tabulated with exact 95% CI by treatment group. Idem for grade 3 AEs, AEs related to vaccination, grade 3 events related to vaccination.

The proportion of subjects with at least one report of unsolicited AE associated to the respiratory system classified by the MedDRA reported during the 90-day post-vaccination follow-up period (on or after Day 0 to Day 89) will be tabulated with exact 95% CI by treatment group, for all subjects in the TVC population.

The same tabulation will be done for, grade 2 or 3 AE associated to the respiratory system, grade 3 AE associated to the respiratory system, AE associated to the respiratory system related to vaccination, grade 2 or 3 AE associated to the respiratory system related to vaccination and grade 3 AE associated to the respiratory system related to vaccination.

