The proportion of subjects with at least one report of grade 3 unsolicited AE associated to the respiratory system classified by the MedDRA reported during the 30-day post-vaccination follow-up period (on or after Day 0 to Day 29) will be tabulated with exact 95% CI by treatment group, for all subjects in the TVC population

Note that the list of preferred terms (PTs) “associated to the respiratory system” is actually the list of PTs which map to the MedDRA System Organ Class (SOC) of “Respiratory, thoracic or mediastinal conditions” regardless if this is their primary SOC or not.

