11.14. Serious adverse events

Percentage of subjects reporting the occurrence of SAEs classified by MedDRA Primary S O C and P T will be tabulated with exact 95% CI by treatment group.

The same tabulations will be done for SAEs with causal relationship to vaccination and for fatal SAEs.

As reporting periods for AE, SAEs and related SAE differ, these tabulations will be done for events occurring during the 30-Day (Days 0-29) post vaccination, during the period from Day 0 to Month 7 and during the entire study period as indicated in the following table.

	Post vaccination period considered		
	30-day post-vaccination period	From Day 0 to Month 7	From Day 0 to end of study*
SAEs	X	X	X**
Related-SAE(s)	X	X	X
Fatal SAE(s)			X

* For the triggered primary analysis: it will be from day 0 to database freeze

** performed only for the CTR tables

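### SAP 11.13 reports respiratory adverse events over 90 days, but most non-serious events are recorded for only 30 days after each dose, and the Grade 2/3 rows have no version matched to that window

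*SAP*

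**What the plan says.** **The 90-day table.** In SAP 11.13, subjects in the TVC with at least one unsolicited respiratory event "reported during the 90-day post-vaccination follow-up period (on or after Day 0 to Day 89) will be tabulated". Five further rows follow: Grade 2 or 3, Grade 3, related, "grade 2 or 3 AE associated to the respiratory system related to vaccination", and related Grade 3. The respiratory term list is wide, since it takes every term that maps to the respiratory class "regardless if this is their primary SOC or not".

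**The 30-day tables.** The general unsolicited tables cover Days 0 to 29 for any event, and "The same tabulations will be done for grade 3 AEs, AEs related to vaccination, grade 3 events related to vaccination" (medically attended events are also covered). The only 30-day table that uses the wide respiratory grouping is for "grade 3 unsolicited AE associated to the respiratory system classified by the MedDRA reported during the 30-day post-vaccination follow-up period".

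**What is recorded.** SAP 4.2 sets the unsolicited endpoint: "During the 30-day follow-up period following vaccination (day of vaccination and 29 subsequent days after each vaccine dose". Protocol 6.6.15 gives the diary-card rule: "Any unsolicited AEs (i.e. on the day of vaccination and during the next 29 days) occurring after vaccination will be recorded by all subjects". Protocol 9.2.1 has the same 30-day limit per dose, Protocol Table 7 schedules unsolicited recording at Visits 2 to 6 only, and Protocol 9.4.1.1 ends review of open events 30 days after the last dose. Three kinds of event are recorded for longer: SAEs, pIMDs whether serious or not, and events leading to withdrawal (Protocol 9.2.1, 9.3.5).

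**Subjects with no report.** SAP 12.3.1 counts them as free of the event, and SAP 12.3.2 takes all vaccinated subjects as the denominator.

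**Origin of the 90 days.** Protocol 6.4.5.4 uses 90 days in its respiratory holding rules. The study-level text counts from any dose; Protocol Table 6 counts from dose 1.

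**The concern.** A proportion labelled 90-day should rest on 90 days of ascertainment. Here most non-serious events have no required recording in part of the window, and the missing-data rule turns unrecorded time into absence of an event with no visible trace. The neighbouring section handles the same issue explicitly: in SAP 11.14, "As reporting periods for AE, SAEs and related SAE differ, these tabulations will be done for events occurring during the 30-Day" and two longer periods. SAP 11.13 makes no such adjustment.

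The rows without a matched version are the ones that correspond to the protocol's Grade 2-or-higher respiratory rules. A reader of the study report who wants the frequency of related Grade 2 or 3 respiratory events would find only the 90-day figure and could take it as complete.

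**Working it through.** **Inputs.** Tabulation window: Day 0 to Day 89 (SAP 11.13). Recording window: Days 0-29 after each dose (Protocol 9.2.1; SAP 4.2). Dose 2 on day d: 26-35 per protocol, 26-50 as the SAP maximum (SAP Table 6).

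**The plan's own figure.** Day 0 to Day 89 inclusive is 89 - 0 + 1 = 90 days, as labelled.

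**Counted from dose 1.** Recorded days are 0-29 and d to d+29. For d = 26 the two stretches share Days 26-29, so 60 - 4 = 56 days are recorded. For d = 30 to 50 they do not overlap, and the last recorded day is at most 50 + 29 = 79, inside the window.

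| Dose 2 | Recorded | Blank | Blank share |
|---|---|---|---|
| Day 26 | 56 | 34 | 34/90 = 38% |
| Day 28 | 58 | 32 | 32/90 = 36% |
| Days 30-50 | 60 | 30 | 30/90 = 33% |
| Not given | 30 | 60 | 60/90 = 67% |

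**Counted from each dose.** The respiratory rows count subjects, so the window for a two-dose subject is the union of both periods: Day 0 to Day d+89, or d + 90 days.

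| Dose 2 | Window | Recorded | Blank share |
|---|---|---|---|
| Day 26 | 116 | 56 | 60/116 = 52% |
| Day 30 | 120 | 60 | 60/120 = 50% |
| Day 35 | 125 | 60 | 65/125 = 52% |
| Day 50 | 140 | 60 | 80/140 = 57% |

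Taken alone, dose 2's own 90 days have 30 recorded and 60 blank (67%).

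**Effect on the proportion.** The documents give no event rates. Assume that the event rate on blank days is k times that on recorded days, and that no ordinary non-serious event is captured on blank days. With R recorded and B blank days, the captured share is f = R/(R + kB).

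| | k = 1 | 0.5 | 0.25 | 0 |
|---|---|---|---|---|
| From dose 1, dose 2 at Day 30 (60, 30) | 67% | 80% | 89% | 100% |
| From each dose, dose 2 at Day 30 (60, 60) | 50% | 67% | 80% | 100% |
| One dose only (30, 60) | 33% | 50% | 67% | 100% |

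For an assumed true proportion p = 5% over the window, the reported value is 1 - (1 - p)^f:
- From dose 1: 1 - 0.95^0.667 = 3.4% (k = 1) to 1 - 0.95^0.889 = 4.5% (k = 0.25).
- From each dose, dose 2 at Day 30: 1 - 0.95^0.5 = 2.5% to 1 - 0.95^0.8 = 4.0%.
- One dose only: 1 - 0.95^0.333 = 1.7% to 1 - 0.95^0.667 = 3.4%.

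**Row by row.**

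| 90-day respiratory row | 30-day version |
|---|---|
| Grade 3 | Yes, same respiratory grouping |
| Any grade; related; related Grade 3 | General MedDRA tables only |
| Grade 2 or 3; related Grade 2 or 3 | None |

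The Grade 2-or-higher tables in SAP 11.11 do not fill the gap. They cover solicited symptoms over 7 days in the sub-cohort.

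**The case against.** The strongest reply is that little information is lost. For dose 2 up to Day 50, every required recording day lies within Days 0-89 from dose 1. The 90-day numerators therefore already contain everything that matched 30-day rows would show, plus a few later SAEs, pIMDs and withdrawal events. This stands: the defect is in what the proportion claims to measure, more than in what it counts.

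Second, the 90-day window is deliberate. It mirrors the protocol's holding rules, and SAP section 14 discloses the added respiratory analysis. Protocol 9.2.1 sets what must be recorded and does not bar later entries. Subjects are asked about TB symptoms and intercurrent conditions at later visits and contacts, and operational detail sits in a manual that is not among the documents. A reader might infer that nothing is captured after the 30-day windows. The documents do not support that. They show only that systematic recording, with grade and causality, is not specified there.

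Third, table layout belongs to a separate list of tables and figures that is also not among the documents, so a suitable footnote may already exist.

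Fourth, a reader might infer that hold decisions are compromised by these tables. They are not. The tables are produced after all Month 24 visits (SAP 13.1), when dosing is over, and the holding rules worked through ad hoc IDMC review during vaccination.

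Finally, limiting the 90-day table to SAEs may look like the clean answer. It would discard valid non-serious data and remove the rows that match the protocol rule.

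**Conclusion.** The mismatch is real and minor. The planned 90-day respiratory proportions are not supported by the planned collection of most non-serious events. The share of the window without required recording is 33-38% from dose 1, or 50-57% of the combined window from each dose, for subjects whose second dose falls on Days 26-50. The 67% figure holds only for one-dose subjects or for dose 2's window taken alone; applying it to all subjects under the each-dose reading would be wrong. These are shares of days. How many events are missed depends on the unknown rate in the blank days and could be close to none if late events are rare.

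A reader might also infer a biased comparison between arms. The documents give no basis for that, because the recording rule is the same in both; what is understated is the absolute frequency. Efficacy is unaffected, as are the serious and fatal holding triggers, since SAEs are recorded to 180 days after the last dose. SAP 13.3 classes these tables as descriptive.

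**What to change.** 1. In SAP 11.13, extend the existing 30-day respiratory table (Days 0-29 after each dose, same wide term grouping) to Grade 2 or 3 and related Grade 2 or 3. For completeness, also add any grade, related, and related Grade 3.
2. Keep the 90-day table, with a footnote that non-serious events were systematically collected only to 30 days after each dose, apart from pIMDs and events leading to withdrawal.
3. State whether Day 0 is dose 1 or each dose.
4. In the study report, state that the 90-day non-serious respiratory holding triggers (any dose in the text of Protocol 6.4.5.4, dose 1 in Protocol Table 6) were not systematically ascertained beyond 30 days after each dose.

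Cost: five table rows, one footnote, one definition and one sentence in the report. No new data are needed.

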11.14. Serious adverse events

Percentage of subjects reporting the occurrence of SAEs classified by MedDRA Primary S O C and P T will be tabulated with exact 95% CI by treatment group.

The same tabulations will be done for SAEs with causal relationship to vaccination and for fatal SAEs.

As reporting periods for AE, SAEs and related SAE differ, these tabulations will be done for events occurring during the 30-Day (Days 0-29) post vaccination, during the period from Day 0 to Month 7 and during the entire study period as indicated in the following table.

	Post vaccination period considered		
	30-day post-vaccination period	From Day 0 to Month 7	From Day 0 to end of study*
SAEs	X	X	X**
Related-SAE(s)	X	X	X
Fatal SAE(s)			X

* For the triggered primary analysis: it will be from day 0 to database freeze

** performed only for the CTR tables

11.15. Potential Immune Mediated Diseases (pIMDs)

The proportion of subjects with at least one report of pIMDs classified by the MedDRA reported during the study period up to 6 months post-dose 2 will be tabulated with exact 95% CI by treatment group.

11.16. Concomitant medication

The number and percentage of subjects with concomitant medication(s), with antipyretics and with immunosuppressant within 30 days post-vaccination will be tabulated with exact 95% CI by treatment group. Concomitant medications will be classified in antipyretics and immunosuppressant according to MedDRA.

11.17. Haematological and biochemical parameters

The analysis of haematological and biochemical parameters will be performed on the safety and immunogenicity sub-cohort.

The frequency distribution of values below and above the site-specific normal ranges will be tabulated per treatment group at each scheduled timepoint (Day 0, Day 7, Day 30 and Day 37).

In addition, change from baseline will also be tabulated by treatment group.

Number and percentage of subjects outside the normal range by severity grading for haematology and biochemistry will be tabulated by treatment group.

For subjects with at least one grade 3 or 4 laboratory value for a specific biochemistry or haematology parameter (TVC), all the values for this specific laboratory parameter will be given for this subject at all timepoints when lab assessments are done

For the toxicity grading scale for haematology and biochemistry, the Food and Drug Administration (FDA) grading for prophylactic vaccine trials was used (Guidance for Industry - Toxicity Grading Scale for Healthy Adult and Adolescent Volunteers Enrolled in Preventive Vaccine Clinical Trials – Sep 2007):

Parameter	Grade 1	Grade 2	Grade 3	Grade 4
Alanine Aminotransferase	[1.1 – 2.6[x ULN	[2.6 – 5.1[x ULN	[5.1 – 10.001[x ULN	\geq 10.001 x ULN
Aspartate Aminotransferase	[1.1 – 2.6[x ULN	[2.6 – 5.1[x ULN	[5.1 – 10.001[x ULN	\geq 10.001 x ULN
Creatinine (mg/dL)	[1.5 – 1.8[[1.8 – 2.1[[2.1 – 2.51[\geq 2.51
Haemoglobin (Change from baseline) (g/dL)	[0.1 – 1.6[[1.6 – 2.1[[2.1 – 5.1[\geq 5.1
Haemoglobin (Decrease) (Female) (g/dL)	[11 – 12.1[[9.5 – 11[[8 – 9.5[< 8.0
Haemoglobin (Decrease) (Male) (g/dL)	[12.5 – 13.6[[10.5 – 12.5[[8.5 – 10.5[< 8.5
Leukocytes (White Blood Cells) (Decrease) (/mm ³)	[2500 – 3501[[1500 – 2500[[1000 – 1500[< 1000
Leukocytes (White Blood Cells) (Increase) (/mm ³)	[10800 – 15001[[15001 - 20001[[20001 - 25001[\geq 25001
Platelets (Decrease) (/mm ³)	[125000 – 140001[[100000 – 125000[[25000 – 100000[< 25000
Bilirubin – when accompanied by any increase in Liver Function Test; increase by factor	1.1 – 1.25 x ULN	1.26 – 1.5 x ULN	1.51 – 1.75 x ULN	> 1.75 x ULN
Bilirubin – when Liver Function Test is normal; increase by factor	1.1 – 1.5 x ULN	1.6 – 2.0 x ULN	2.0 – 3.0 x ULN	> 3.0 x ULN

ULN = upper limit of the normal range.

The bilirubin grading scale at a given time-point will depend on the liver function tests (ALT and AST) at the corresponding time-point. When both liver function tests are normal, i.e. when ALT and AST are grade 0 according to the FDA grading (reference: *FDA Guidance for Industry: Toxicity Grading Scale for Healthy Adult and Adolescent Volunteers Enrolled in Preventive Vaccine Clinical Trials (September 2007)*), the “Bilirubin – when Liver Function Test is normal” scale will be applied while when at least one of the liver function tests (ALT or AST) is grade 1 or above, the “Bilirubin – when accompanied by any increase in Liver Function Test” scale will be applied. In the descriptive analysis, the bilirubin grades will be presented together regardless of the scale used.

Vitamin D is measured at screening in all subjects of the immuno and safety sub-cohort. Levels will be summarized by mean, standard deviation, minimum, Q1, median, Q3 and maximum by group at baseline inside the safety and immunogenicity sub-cohort.

The number and percentage of subjects with vitamin D deficiency in the immune and safety sub-cohort will be tabulated where Vitamin D deficiency is defined as serum 25(OH) D concentrations : < 20 ng/mL.

One laboratory parameter is analysed independently of the sub-cohort:

HbA1C is measured in confirmed TB cases. For those subjects, the descriptive statistics (N, mean, standard deviation, min, Q1, median, Q3, max) will be displayed by group.

11.18. Performance of culture and GeneXpert test

For all the suspicions of pulmonary TB, the result (positive/negative) for GeneXpert will be tabulated by result for culture (positive/negative) for all the pairs of results which are both available, without split by vaccine group.

This cross table will be performed without split by vaccine group as well for all suspicions which lead to treatment for TB and then further split with respect to timing of the sputum sample, so when sputum sample is taken on or before TB treatment start and separately when sputum sample is taken after TB treatment start.

12. STATISTICAL CALCULATIONS

12.1. Demography

12.1.1. Derived and transformed data

Age at the reference activity will be computed as the number of units between the date of birth and the reference activity. In case of partial dates of any of these 2 dates, the following reference dates will be used:

- 15th of month, if only the day is missing.
- 30th of June, if the day and month are missing.

12.2. Immunogenicity

12.2.1. Handling of missing data

For a given subject and a given immunogenicity measurement, missing or non-evaluable measurements will not be replaced.

Therefore, an analysis will exclude subjects with missing or non-evaluable measurements.

